**Specific Aim 1:** To determine whether varenicline pharmacotherapy is enhanced by either a nicotine replacement adjuvant (i.e., patch NRT) or extended medication duration (i.e., 24 vs. 12 weeks postquit). The effects of these pharmacotherapy strategies will be reflected in main effects for both experimental factors, and in direct comparisons of the enhanced varenicline conditions with standard 12-week varenicline-only. The primary outcome will be 52-week biochemically confirmed smoking abstinence (7-day point-prevalence).

**Specific Aim 2:** To determine the effects of the varenicline conditions on additional critical outcomes such as 23-week point prevalence and prolonged abstinence, smoking cessation milestones (abstinence, latency to lapse, and lapse-relapse latency), cost-effectiveness, withdrawal severity, and adverse events. The variables that mediate and moderate (e.g., genotype) the effects of the different pharmacotherapies will also be identified.

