the latter identifies the most robust interactions amongst subpopulations of a sample (groups of participants nested within levels of another predictor, which could include either a covariate or treatment condition). Candidate moderators of treatment effects on abstinence will include tobacco dependence, contextual factors such as household smoking, and biological variables such as sex and genotype. In the logistic regression analyses moderators will be evaluated with regards to their interactions with treatment main effects and interactions.

**Cost-Effectiveness:** Cost-effectiveness of key comparison treatments will be evaluated using methods recommended by the United States Panel on Cost-Effectiveness in Health and Medicine and consistent with our prior research in this area. We will: (1) measure all costs from the societal perspective; (2) convert cost estimates to a common year; (3) use a rate of 3% to discount future outcomes and costs to present value; (4) use QALYs as the outcome metric; and (5) conduct Monte Carlo sensitivity analyses. The proposed research will cost out all intervention component combinations that reflect significant main and synergistic interaction effects. We will determine net monetary benefit (NMB), cost per quit, and incremental cost-effectiveness ratios (ICERs). The components of NMB will be the added costs of the treatments and the monetized value of the QALYs added by the treatments. Using methods described by Stapleton, we will convert the increased effectiveness of the treatments from quits to added QALYs.

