The predicted data would strongly implicate the additive effects of both 24-week duration and the P adjuvant as being necessary to achieve a marked increase in abstinence over standard V-based therapy. Of course, we might discover instead that a single treatment modification or enhancement confers as much benefit as the combination of the two components (e.g., 24-week V-only produces as much benefit as 24-week V+P). This finding would be welcome to the extent that it means that exceptionally strong results are obtained with the use of only one treatment enhancement, which would save money and perhaps reduce adverse events and burden.

**Statistical Power:** We computed power (via SAS PROC POWER) for the abstinence outcomes in Table 4, assuming  $p < .05$  and two-tailed tests. Power is .88 for the main effect for Duration (n's=625), and .97 for the main effect of Varenicline (V+P vs. V: n's=625). Moreover, power is  $> .99$  for the key hypothesis that the 24-week V+P combination will be superior to 12-weeks of V-only (n's=312). The N used clearly provides some room for error if the predicted outcomes are too sanguine. For instance, we noted above that some data suggest that the increase in abstinence seen with extended medication might be as small as 7%. The proposed N (1250) would permit detection of a 7 point difference with power = .80. Thus, the N proposed would provide good power to detect the proposed effects, and even effects that are modestly weaker, but still of public health significance.

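### The cost-effectiveness analysis ties what is costed to statistical significance and to synergistic interactions, a condition that Aim 2 does not set

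*Combined protocol and SAP*

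**What the plan says.** The Cost-Effectiveness paragraph (Analytic Approach) opens with its scope: "Cost-effectiveness of key comparison treatments will be evaluated using methods recommended by the United States Panel on Cost-Effectiveness in Health and Medicine". Key comparison treatments are not defined. The one later sentence that says what will be costed is that the research will "cost out all intervention component combinations that reflect significant main and synergistic interaction effects". The outputs are net monetary benefit, cost per quit and ICERs, and for the health gain "we will convert the increased effectiveness of the treatments from quits to added QALYs". For uncertainty, the plan is to "conduct Monte Carlo sensitivity analyses".

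Specific Aim 2 (Study Overview) is wider. It is "To determine the effects of the varenicline conditions on additional critical outcomes", and the list includes "cost-effectiveness, withdrawal severity, and adverse events". No test result is required there.

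The Cessation paragraph sets out two analyses of abstinence: a factorial model with main effects and interaction, and a comparison of each enhanced arm with 12-week V-only. The costing sentence does not say which of the two supplies its significance tests.

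**The concern.** An ICER or a net monetary benefit is a function of expected cost and expected effect. A non-significant gain is not a zero gain, and an arm that misses p<.05 may still be the best value. A significance gate on costing has three consequences.

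- An arm may get no estimate. Each option is compared with the next less costly one that is not dominated, so losing a single-enhancement arm also changes the comparator for the combination.
- Reporting becomes selective. Gains reported only when significant are too large on average, and those gains are what is converted to QALYs.
- Only synergistic interactions are named. A less-than-additive interaction is where paying for both enhancements may buy little over one, and the costing rule does not mention it.

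The power section itself says that it would be good news if one enhancement did as well as both, partly because money would be saved. That conclusion needs the single-enhancement arms to be costed.

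**Working it through.** **Inputs.** Table 4 rates, 312 per arm: 12-week V-only 25.0%, 12-week V+P 34.0%, 24-week V-only 32.0%, 24-week V+P 44.9%. The combination column is headed V+ML and is taken here as V+P. Marginals: Duration 29.5% vs 38.5%, Adjuvant 28.5% vs 39.4%. Two-sided alpha .05, from the Statistical Power paragraph.

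**Formula.** With p̄ the mean of p1 and p2 and n per group, power = Φ{[|p1 − p2| − 1.96·√(2p̄(1 − p̄)/n)] / √([p1(1 − p1) + p2(1 − p2)]/n)}.

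**1. The plan's own figures (n=625 per level).**
- Duration: (0.09 − 1.96 × 0.02680)/0.02668 = 1.40, so power is .92. The plan states "Power is .88 for the main effect for Duration".
- Adjuvant: (0.109 − 1.96 × 0.02679)/0.02661 = 2.12, so .983 (stated .97).
- 24-week V+P vs 12-week V-only, n=312: .9996 (stated >.99).

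The Duration figure is not reproduced at n=625. With n=550 per level the formula gives .884 and .969. That is a separate matter and does not affect this point.

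**2. Factor-level gate, Table 4 true.** Simulated trials with 312 per arm; an effect passes if two-sided p<.05 in the beneficial direction.
- Duration passes 92%, Adjuvant 98%, both 90%, so at least one fails in about 10%.
- Given that Duration passes, the mean gain of 24-week V-only over standard is 7.4 points against a true 7.0 (1.06 times).
- Given that Adjuvant passes, the mean gain of 12-week V+P is 9.1 against 9.0 (1.01 times).

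**3. Arm-level gate, Table 4 true (n=312).**
- 24-week V-only vs standard: (0.07 − 1.96 × 0.03614)/0.03603 = −0.02, so it passes 49%. Mean gain given a pass is 9.9 points against 7.0 (1.42 times).
- 12-week V+P vs standard: (0.09 − 1.96 × 0.03651)/0.03633 = 0.51, so it passes about 70%. Mean gain given a pass is 10.8 against 9.0 (1.20 times).
- 24-week V+P passes almost always, with no material inflation.

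This reading is not far-fetched. The plan uses dummy coding with the interaction in the model. With 0/1 coding, each so-called main-effect coefficient is then the simple effect at the reference level of the other factor. On the log-odds scale those two tests have power .49 (Duration) and .69 (Adjuvant).

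**4. Assumption: effects half of Table 4** (25, 29.5, 28.5 and 34.95%, in the order of the inputs). Factor-level gate: Duration passes 41% and Adjuvant 57%; at least one fails in about 77% of trials and neither passes in 26%. Given a pass, the main-effect estimates average 1.55 and 1.33 times the truth.

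**5. Assumption: antagonistic pattern** (25, 34, 32 and 34%). The interaction is significantly antagonistic in 29% of trials and significantly synergistic in 0.04%. Neither main effect passes in 32%, although every enhanced arm truly gains 7 to 9 points.

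**6. Why the comparator matters.** At Table 4 rates the combination gains 44.9 − 25.0 = 19.9 points over standard, but 44.9 − 34.0 = 10.9 over 12-week V+P and 44.9 − 32.0 = 12.9 over 24-week V-only. Dropping a single-enhancement arm can therefore change the denominator of the combination's incremental ratio substantially. The documents give no costs, so the ratio itself cannot be computed.

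**The case against.** The strongest reply is that the sentence uses factorial terms, main effects and interaction, and that main effects are powered on 625 per level. On that reading the gate seldom bites if Table 4 is right. Even when the 24-week V-only contrast is not significant, the Duration main effect passes in 85% of trials. This stands, and it means the arm-level figures cannot be presented as the effect of the rule. They are one of two readings.

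It can also be said that the sentence does not restrict costing to these combinations in so many words, that the scope phrase is undefined, and that Aim 2 covers all conditions. This leaves room for a wider analysis but does not commit anyone to it.

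Three stronger inferences are tempting and are not supported:

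- *The trial could not say which of its four treatments is best value.* If both factors pass (90% at Table 4 rates), all three enhanced arms qualify, and the standard arm is needed as comparator.
- *Antagonistic interactions are skipped.* A combination can also qualify through a main effect. In the antagonistic pattern above at least one passes in 100 − 32 = 68% of trials, and the abstinence analysis examines interactions in either direction. What is missing is any statement that the costing then uses each arm's own result.
- *Costing every arm would correct an inflated estimate.* In a trial where an arm passes, its estimate is the same either way. What changes is which results are reported.

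**Conclusion.** The point holds as a defect of scope. The only operative sentence conditions costing on significance and synergy, narrows Aim 2, and can remove options that an incremental analysis needs. Its size ranges from small (factor-level gate with Table 4 true: about a 10% chance that a factor fails, single-enhancement gains inflated by about 6% and 1%) to substantial (arm-level gate, or true effects well below Table 4). Weaker effects are plausible on the protocol's own account: it cites a gain of about 5 points for extended patch and says that little is known about extended varenicline. The half-effect and antagonistic scenarios are assumptions, not predictions of the plan. The point concerns a secondary aim. The primary abstinence analysis, the randomisation and the data collection are unaffected. It should be put right before the analysis, but it is not critical.

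**What to change.** Strike the condition on significance and synergy from the sentence that plans to "cost out all intervention component combinations that reflect significant main and synergistic interaction effects". State instead that costs and QALYs will be estimated for all four arms whatever the test results, using each arm's own estimated effect. Report incremental net monetary benefit, and ICERs for each arm against the next less costly non-dominated arm, with uncertainty from the Monte Carlo analysis already planned.

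This removes selective reporting and missing options, and it lets a less-than-additive combination show its value. It costs a change of wording and a little more analysis. Table 2 sets one schedule of contacts and assessments for all participants, so no further data collection is needed.

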**PROTOCOL**  
“Quitting Using Intensive Treatment Study (QUITS)”  
PI: [name] and [name] ; UW-CTRI Grant:

In terms of the effects of increased duration of medication use, Schnoll et al., found that 24 versus 8 weeks of nicotine patch increased abstinence rates by only about 5 percentage points at 52-week follow-up. However, extended V treatment (24 weeks total) increased abstinence rates at 52 weeks post-TQD by about 10 percentage points in one study just among patients who were abstinent early in treatment, and by about 40 percentage points in another, smaller study. We believe that extended medication will increase abstinence rates by 7-11 percentage points (with regard to the V-only and V+P conditions, respectively) because research shows that extended pharmacotherapy both reduces relapse in those who are abstinent and increases the likelihood of cessation amongst those who have lapsed. Moreover, both NRT and V produce such effects, thus, these actions could be additive in those using both active agents. Because of the possibility of an additive effect, we posit slightly higher increases in Duration-related abstinence rates for the V+P condition than for the V-only condition. However, the uncertainty about the effect of Duration highlights the innovativeness of this work; we know very little about the effects of extended V treatment and nothing about the effects of extended V+NRT treatment. While the abstinence rates forecast may seem high, we believe they are reasonable given that they reflect the effects of 3 pharmacotherapy elements or dimensions (varenicline therapy, 24 week duration, and an NRT adjuvant) all supported by evidence of efficacy. The predicted outcomes result from the reasonable assumption that these 3 components will produce at least additive effects.

The predicted data would strongly implicate the additive effects of both 24-week duration and the P adjuvant as being necessary to achieve a marked increase in abstinence over standard V-based therapy. Of course, we might discover instead that a single treatment modification or enhancement confers as much benefit as the combination of the two components (e.g., 24-week V-only produces as much benefit as 24-week V+P). This finding would be welcome to the extent that it means that exceptionally strong results are obtained with the use of only one treatment enhancement, which would save money and perhaps reduce adverse events and burden.

**Statistical Power:** We computed power (via SAS PROC POWER) for the abstinence outcomes in Table 4, assuming  $p < .05$  and two-tailed tests. Power is .88 for the main effect for Duration (n's=625), and .97 for the main effect of Varenicline (V+P vs. V: n's=625). Moreover, power is  $> .99$  for the key hypothesis that the 24-week V+P combination will be superior to 12-weeks of V-only (n's=312). The N used clearly provides some room for error if the predicted outcomes are too sanguine. For instance, we noted above that some data suggest that the increase in abstinence seen with extended medication might be as small as 7%. The proposed N (1250) would permit detection of a 7 point difference with power = .80. Thus, the N proposed would provide good power to detect the proposed effects, and even effects that are modestly weaker, but still of public health significance.

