### **Analytic Approach**

**Cessation:** The primary outcome (biochemically confirmed, self-reported point-prevalence abstinence at 52 weeks post-TQD) will be analyzed via two strategies. First, we will conduct factorial design analyses using logistic regression with dummy coding that examines

PROTOCOL  
“Quitting Using Intensive Treatment Study (QUITS)”  
PI: [name] and [name] ; UW-CTRI Grant:

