the main and interactive effects of the two factors. Importantly, main effects obtained with dummy coding in 2-factor designs are directly interpretable even in the presence of a significant interaction as long as the interaction effect is included in the model. Thus, main effects will reflect the effects of V+P vs. V-alone, and the effects of 24- vs. 12-week treatment duration. Interaction effects would reveal whether the magnitude of differences in effects of the levels of V treatment varies in a multiplicative manner depending on duration. While we hypothesize that we will see only main effects in this research, interactions would be interpreted via visual inspection (the highest and lowest scores for the interacting treatment combinations should be readily apparent) and via simple effects tests. Second, we will conduct analyses typical of an RCT, which use logistic regression models with dummy coding to contrast each of the three enhanced varenicline treatments (12-week V+P, 24-week V-only and 24-week V+P) with the standard V-based treatment (12-week V-only). The V-only condition will serve as the reference condition because the intent is to determine if any of the enhanced V-based treatments is superior to that condition. Covariates will include sex, race, treatment site, and level of tobacco dependence (FTND item 1). Results will be reported with and without covariate adjustment and the specific effects of sex and race on each outcome will be explored. The same analytic approach will be used for secondary abstinence analyses (e.g., point-prevalence at 6-months and prolonged abstinence). The intent-to-treat principle with the assumption of missing-smoking will be used for abstinence analyses but will be supplemented with sensitivity analyses and multiple imputation for missing data to support scientific rigor. The latter models will assume that 80% of dropouts return to smoking and that abstinence likelihood is related to baseline smoker covariates. Analyses of secondary abstinence outcomes will support scientific rigor by controlling for experiment-wise error in families of related tests. Milestones analyses will be conducted as in our prior research. For instance, latency between initial abstinence and lapsing, and latency between lapsing and relapse, will be computed with Cox proportional hazards regression/survival models.

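### The Duration power of .88 does not reproduce (about .92 on the plan's own inputs), the 7-point fallback names no baseline, and the powered contrasts are not those a dummy-coded model with interaction tests

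*Combined protocol and SAP*

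**What the plan says.** The Statistical Power paragraph reports SAS PROC POWER results for the Table 4 rates at p<.05, two-tailed. It states: "Power is .88 for the main effect for Duration (n's=625" per level), .97 for patch against no patch (called the main effect of Varenicline, also 625 per level), and more than .99 for 24-week V+P against 12-week V-only (312 per cell). It does not name the test.

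As room for error it adds that "The proposed N (1250) would permit detection of a 7 point difference with power = .80", with no baseline rate. It introduces the 7 points by saying that "some data suggest that the increase in abstinence seen with extended medication might be as small as 7" per cent. The text just before it presents 7 as the lower end of a forecast, the V-only figure: "We believe that extended medication will increase abstinence rates by 7-11 percentage points". The paragraph concludes that "the N proposed would provide good power to detect the proposed effects" and somewhat weaker ones.

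For the primary outcome, the Analytic Approach (Cessation) says "we will conduct factorial design analyses using logistic regression with dummy coding that examines" main and interactive effects. It adds that "main effects obtained with dummy coding in 2-factor designs are directly interpretable even in the presence of a significant interaction", provided the interaction is in the model. A second analysis will "contrast each of the three enhanced varenicline treatments" with 12-week V-only.

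**The concern.** This paragraph is the plan's justification of N and of its margin for error. It states rates, group sizes, alpha and sidedness, so the .88 should reproduce closely under any standard two-group test. The 7-point claim cannot be checked as written, because power for a fixed difference depends on the baseline rate.

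The third issue concerns what will be tested. Group sizes of 625 imply a comparison of margins that pools over the other factor. With 0/1 dummy coding and the interaction in the model, a factor's coefficient instead compares two cells at the reference level of the other factor. If the Duration result were read from that coefficient, it would rest on half the sample and answer a narrower question than the one powered.

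**Working it through.** **Inputs.** Table 4 cells: 12-week V-only 25.0%, 12-week V+P 34.0%, 24-week V-only 32.0%, 24-week V+P 44.9% (the V+P column is headed V+ML). Duration margins are 29.5% and 38.5%; adjuvant margins are 28.5% and 39.4%. There are 625 per level and 312 per cell; alpha is .05, two-sided.

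**Formula for two proportions** (Pearson, pooled null variance). With d = p2 − p1 and p̄ their mean: s0 = √[2p̄(1−p̄)/n], s1 = √[(p1(1−p1)+p2(1−p2))/n], power = Φ[(d − 1.96·s0)/s1].

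**1. The stated figures**
- Duration: p̄ = .340, s0 = .02680, s1 = .02668. (.090 − .0525)/.02668 = 1.405, so power is **.920**, against .88 stated. Continuity-corrected and Fisher exact give .911, and a Wald test on the log odds ratio .918. Every two-sided .05 variant tried at 624–625 per level fell between .909 and .921.
- Patch: s0 = .02679, s1 = .02661. (.109 − .0525)/.02661 = 2.12, so power is **.983**, against .97 stated.
- 24-week V+P against 12-week V-only, n=312: **.9996**, so the stated >.99 is right.
- At 550 per level the first two become .884 and .969, which round to the stated pair.

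**2. Seven points at 625 per level**

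| Baseline | Source | Power |
|---|---|---|
| 34% | Table 4, 12-week V+P | .725 |
| 29.5% | Table 4, 12-week margin | .750 |
| 25% | Table 4, 12-week V-only | .783 |
| about 23% | none; solved for .80 | .80 |
| 19% | V-only in the team's recent trial (Statistical Power for Primary Outcome) | .843 |

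For a Duration main effect the matching baseline is the 12-week margin, 29.5%. From there, 80% power needs 7.46 points.

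**3. What each coding tests.** Cell log-odds, in the order 12-week V-only, 12-week V+P, 24-week V-only, 24-week V+P, are −1.0986, −.6633, −.7538 and −.2047. Their variances, 1/[312·p(1−p)], are .01709, .01428, .01473 and .01296. Wald power is Φ(estimate/SE − 1.96).

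Effect coding averages the two simple effects, with SE = √(.05906/4) = .1215:
- Duration: (.3448 + .4586)/2 = .4017; ratio 3.31; power **.911**.
- Patch: .4922; ratio 4.05; power **.982**.

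With 0/1 coding and the interaction, each coefficient is one simple effect:

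| Coefficient | Reference level of the other factor | Estimate | SE | Power |
|---|---|---|---|---|
| Duration | V-only (25% vs 32%) | .3448 | .1784 | .49 |
| Duration | V+P (34% vs 44.9%) | .4586 | .1650 | .79 |
| Patch | 12 weeks (25% vs 34%) | .4353 | .1771 | .69 |
| Patch | 24 weeks (32% vs 44.9%) | .5491 | .1664 | .91 |

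The .49 and .69 rows are also two of the three planned contrasts with 12-week V-only (chi-square .491 and .694). The paragraph gives no power for either.

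**The case against.** The only figure that plainly fails to reproduce understates power, so correcting it strengthens the case for N. The .97 against .98 is trivial.

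The .80 is not shown to be false on every reading. The plan ties 7 points to V-only, where the 12-week rate is 25% and power is .783, within 2 points of .80. The sentence covers the case where predictions are too optimistic, and from the 19% V-only rate power is .84. That stands. But those are V-only rates, whereas the claim is made for N=1250, that is, for the pooled Duration effect. Its Table 4 baseline gives .75.

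On coding, the plan states its intended comparisons (V+P against V alone, 24 against 12 weeks), and 625 per level points to margins. V-only is named as reference only for the second, RCT-style analysis. A reader might therefore infer too much from .49: it is not the power of the Duration main effect, and it holds for the dummy-coded coefficient only if V-only is the reference level. The mismatch between the stated model and the powered contrast remains under either reference level. Coding does not explain the .88, since neither coding produces it.

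The plan calls only 24-week V+P against 12-week V-only its key hypothesis and claims no figure for the other two contrasts. Giving their power is thus an addition. It is still useful, because Specific Aim 1 includes direct comparisons of the enhanced conditions with standard treatment.

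**Conclusion.** The point holds as a reporting and specification fault. At the Table 4 rates, Duration power is .91–.92, not .88, and patch power is about .98. The 7-point claim overstates power by about 5 points for the pooled Duration effect (.75 against .80) and by under 2 points from 25%. It is met only from a baseline of about 23% or lower. The powered marginal contrasts are not what 0/1 coefficients test once the interaction is included: there, power is .49 or .79 for Duration and .69 or .91 for patch, with the reference level unstated.

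Two stronger readings are not supported. One is that N=1250 is too small: at the Table 4 rates it is ample for both marginal main effects and for 24-week V+P against 12-week V-only. The other is that the figures were carried over from N=1100. The match at 550 per level, the mention of a new enrollment goal under Table 4, and the figure of 1100 consented in Protection of Human Subjects are suggestive, but the documents do not say so and no correction depends on it.

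The description of 7 points as coming from data is a minor wording matter. The results cited just before are about 5, 10 and 40 points, and 7 is the investigators' forecast.

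**What to change.** In Statistical Power:
- Rerun the calculation and name the test. Restate Duration as about .91–.92 and patch as about .98.
- Name the baseline for the 7-point claim. For the Duration main effect give .75 from 29.5%, with 80% power at about 7.5 points. Call 7 points the investigators' forecast.
- Limit the claim of good power to the two marginal main effects and 24-week V+P against 12-week V-only. Add about .69 (12-week V+P) and .49 (24-week V-only) for the other two contrasts with 12-week V-only.

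In Analytic Approach:
- Specify effect coding, or a marginal contrast from the fitted model, for the two main effects, so that the test matches the powered comparison. If dummy coding is kept for other purposes, state its reference levels.

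The cost is a short rerun and text edits. N, design and data collection do not change. The coding should be settled before the primary analysis.

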**Table 2. Schedule of Study Activities**

	Pre-Cessation	Treatment Phase						Phone Follow-up				
		V1	C1	V2	V3	C2	C3	C4	C5	C6 	C7	C8 
Week	Orientation	Wk - 2	-1	TQD	2	4	8	11	17	23	39	52
Screening & Informed consent	X											
Randomization	X											
Pre-cessation counseling		X	X									
Cessation counseling				X	X	X	X					
Exhaled CO	X	X		X	X					X 		X 
Short questionnaire on CO exposure	X	X		X	X					X 		X 
Smoking status	X	X	X	X	X	X	X	X	X	X	X	X
Blood sample for DNA/RNA and cotinine		X										
Non-cigarette nicotine use	X	X		X		X	X			X		X
Baseline questionnaires	X	X										
IVR assessments	X	X	X	X	X							
Treatment mechanisms assessment 		X	X	X	X	X	X	X	X	X	X	X
Medication provision		X		X			X					
Medication use assessment			X	X	X	X	X	X	X	X	X 	
Adverse events			X	X	X	X	X	X	X	X	X	X

If participants claim abstinence during this assessment call, they will be invited to an in-person visit to provide biochemical verification of abstinence (CO assessment).

Treatment mechanisms include withdrawal, affect, fatigue, cigarette liking/effects, stressors, cue exposure, motivation, and self-efficacy.

Timeline follow back only

week post-quit). Per our intention-to-treat data analysis plan, any randomized smoker who does not provide biochemically confirmed evidence of abstinence will be counted as a smoker; multiple imputation also will be performed in secondary analyses to further enhance scientific rigor. A daily smoking calendar will permit determination of lapse/relapse latencies for survival and milestones analyses. In order to enhance *scientific transparency*, we will post all assessment instruments and, ultimately, de-identified data, online (e.g., the UW-CTRI website; average of 7,000 hits/month over last year from 17,387 visitors), so that other researchers can use our de-identified data and instruments (see detail in Data Sharing Plan).

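### The power section credits cited data with a 7-point minimum gain from extended medication, but 7 is the low end of the investigators' forecast; the lowest cited figure is about 5 points, where power is about one half

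*Combined protocol and SAP*

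**What the plan says.** The Statistical Power paragraph (under Analytic Approach) assumes p < .05 "and two-tailed tests" and reports: "Power is .88 for the main effect for Duration (n's=625"). It then argues that the sample size tolerates forecasts that prove too optimistic. Its one worked example concerns Duration: it refers back to earlier text and says that "some data suggest that the increase in abstinence seen with extended medication might be as small as 7"%, followed by "The proposed N (1250) would permit detection of a 7 point difference with power = .80".

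The earlier text is the discussion of medication duration in Statistical Power for Primary Outcome, after Table 4. It describes three results:

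- an extended-patch trial in which "24 versus 8 weeks of nicotine patch increased abstinence rates by only about 5 percentage points at 52-week follow-up";
- extended varenicline, which raised 52-week abstinence "by about 10 percentage points in one study just among patients who were abstinent early in treatment";
- a second, smaller varenicline study with a gain of about 40 points.

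The investigators' own forecast follows: "We believe that extended medication will increase abstinence rates by 7-11 percentage points", the lower figure for varenicline alone and the higher for varenicline plus patch. Table 4 carries the same forecast. Varenicline alone goes from 25.0% to 32.0%, and the marginals go from 29.5% (12 weeks) to 38.5% (24 weeks).

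**The concern.** The sentence presents 7 points as what data suggest the gain could fall to. The data to which it points are 5, 10 and 40. The only 7 for Duration in that discussion is the bottom of the investigators' forecast. A forecast value has therefore been given the standing of an empirical lower bound, and the lowest empirical figure that the plan cites has no power attached to it.

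Duration is one of the two factors in Specific Aim 1, and the plan itself stresses how uncertain its effect is. The .80 is the only power figure offered for a Duration effect smaller than planned. A reader who takes it as covering the lowest value in the evidence could later read a non-significant Duration result as showing no useful gain, when a gain of about 5 points would be missed about half the time.

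**Working it through.** **Inputs.** Two-sided alpha .05, so z = 1.96, and n = 625 per Duration level (Statistical Power). The base rate is either 29.5%, the 12-week marginal in Table 4 and so the natural base for the main effect, or 25%, the 12-week varenicline-only cell. The plan does not say which base its .80 uses. There is no dropout inflation, because "any randomized smoker who does not provide biochemically confirmed evidence of abstinence will be counted as a smoker", so all 625 stay in the denominator.

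**Formula.** For two proportions p1 and p2 with d = p2 − p1 and pbar = (p1 + p2)/2:

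- SE0 = √[2·pbar(1 − pbar)/n]
- SE1 = √[(p1(1 − p1) + p2(1 − p2))/n]
- power = Φ[(d − 1.96·SE0)/SE1]

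**Step 1: the plan's figure for 7 points.**

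- From 25% to 32%: SE0 = .02554, SE1 = .02546. (.070 − .05005)/.02546 = 0.784; power .783.
- From 29.5% to 36.5%: SE0 = .02660, SE1 = .02653. (.070 − .05213)/.02653 = 0.674; power .750.

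The stated .80 is roughly right for 7 points from 25% and somewhat high from 29.5%.

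**Step 2: the same calculation for 5 points.**

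- From 25% to 30%: SE0 = .02526, SE1 = .02522. (.050 − .04951)/.02522 = 0.020; power .508.
- From 29.5% to 34.5%: SE0 = .02639, SE1 = .02635. (.050 − .05172)/.02635 = −0.065; power .474.

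Power is near one half because an observed difference must reach about 5 points (1.96 × SE0) to be significant, and a true gain of 5 points sits at that threshold. Fisher-type or continuity-corrected versions give .48 and .45.

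**Step 3: smallest difference with 80% power.** Solving for d gives 7.2 points from 25% and 7.5 points from 29.5%.

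| True Duration gain | Base 25% | Base 29.5% |
|---|---|---|
| 7 points (low end of forecast) | .78 | .75 |
| 5 points (lowest cited result) | .51 | .47 |
| Gain detectable with 80% power | 7.2 points | 7.5 points |

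**Step 4: where 7 comes from.** Table 4, varenicline alone: 32.0 − 25.0 = 7 points. Table 4, marginals: 38.5 − 29.5 = 9 points. So 7 is the smaller of the two forecast simple effects and lies 2 points below the planned main effect. It matches none of the three cited results.

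**The case against.** Four points can be made for the plan.

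1. **Seven is a weaker case than the one planned.** This stands. The planned main effect is 9 points, so 7 is a reduction, and the conclusion that the paragraph draws is confined to modestly weaker effects. It would be wrong to call 7 the central prediction for the main effect, although a reader might take it so because it equals the varenicline-only difference.
2. **The 5-point result may not transfer.** It comes from nicotine patch alone, 24 versus 8 weeks, and the plan goes on to contrast it with larger varenicline results. This also stands, and for that reason 5 should not simply replace 7 as the lower bound. However, the plan introduces the result as evidence on medication duration, and the power sentence speaks of extended medication in general. If the patch result is set aside, the remaining figures are 10 and 40, and 7 still has no source in the data.
3. **The .80 is not a miscalculation.** Agreed. A reader might set .80 against .47 and infer an arithmetic error, but those figures belong to different effects and, in all likelihood, different base rates. The fair comparisons are .78 with .51, or .75 with .47.
4. **The uncertainty about Duration is disclosed.** It is, but in words. The only number given for a smaller effect is the .80.

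A reader might also argue that the 10-point varenicline result, being confined to early abstainers, shrinks to about 5 points over all randomised smokers. The documents do not support this. They give no early-abstainer proportion, and the step assumes no benefit in everyone else, whereas the plan states that extended treatment also helps people who have lapsed to quit.

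**Conclusion.** Wrong as written, in attribution and in what the robustness example covers. The 7-point figure is the investigators' lower forecast, not a value suggested by the data described. At the smallest gain the plan cites, about 5 points, the Duration main effect has power of about .47 (base 29.5%) to .51 (base 25%), against .75 to .78 for 7 points on the same bases. With 625 per level the trial has 80% power only for a gain of about 7.2 to 7.5 points, so the margin below the 9-point plan is about 1.5 to 1.8 points.

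This rests on an unadjusted comparison of the two Duration marginals with 625 each, as the plan's own power statement implies, and on the base rates in Table 4. The conclusion is the same on either base. It does not show that 5 points is the right lower bound for varenicline-based treatment, nor that the sample size is inadequate for the planned effect.

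**What to change.** In the Statistical Power paragraph:

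- Attribute 7 points to the lower end of the 7 to 11 point forecast, and state its base rate and power: .75 from the 29.5% main-effect base, .78 from 25%.
- Add the power for the 5-point result already cited (.47 from 29.5%, .51 from 25%), noting that it comes from patch alone at 24 versus 8 weeks. If the investigators judge that it does not apply to varenicline-based treatment, say so and why.
- State the smallest Duration difference detectable with 80% power: about 7.5 points from 29.5%, about 7.2 from 25%.
- Limit the claim of slack for Duration to that range, and add that a non-significant Duration result will not be read as excluding a gain of about 5 points.

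The cost is a few sentences and a less favourable stated figure. Sample size, analysis and conduct do not change.
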